2.3 Rationale

The main purpose of the study is to estimate the ability of talimogene laherparepvec administered prior to surgery to increase RFS in subjects with resectable stage IIIB to IVM1a melanoma.

It is expected that neoadjuvant treatment with talimogene laherparepvec will improve both local and distant control by achieving higher rates of tumor-free (negative) margin surgical resection (R0), and will decrease distant metastasis rate through systemic effects on micrometastatic disease.

Since talimogene laherparepvec is assumed to work via activation of the immune system and infiltrating T cells have also been shown to be prognostic for melanoma ([Erdag et al, 2012](#)), it is important to understand whether the number and type of tumor infiltrating and peripheral immune cells impact drug efficacy. Therefore, tumor and blood samples will be collected before and at the end of the talimogene laherparepvec treatment to investigate the relationship between the activities of the immune system, such as cytotoxic CD3+/CD8+ and CD8+/CD45R0 T-lymphocytes, tumor antigen specific T cells, regulatory T cells and myeloid-derived suppressor cells measured both in the tumor and/or in the peripheral blood, and response to the treatment. Additionally, a number of immune-related biomarkers, such as antibodies to melanoma antigens and expression of immune-stimulatory and immune-inhibitory molecules (eg CTLA-4,

program cell death-1 [PD-1], program cell death-1 ligand 1 [PD-L1] and others) in tumors or tumor infiltrating T-cells will be assessed to determine any association with clinical outcomes.

Moreover, tumor biopsy samples will be assessed for mutations effecting viral replication, such as double-stranded RNA-activated protein kinase (PKR) that cells activate to protect themselves from viral infection and whose activity may predict clinical response to treatment with talimogene laherparepvec. Also, safety of talimogene laherparepvec, especially related to postoperative complications will be evaluated.

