9.2 Reporting of Adverse Events

9.2.1 Reporting Procedures for Adverse Events That do not Meet Serious Criteria

The investigator is responsible for ensuring that all adverse events observed by the investigator or reported by the subject that occur after randomization through the safety follow-up visit (ie, 30 [+15] days after surgery) are reported using the applicable CRF (eg, Adverse Event Summary).

The investigator must assign the following adverse event attributes:

- Adverse event diagnosis or syndrome(s), if known (if not known, signs or symptoms),
- Dates of onset and resolution (if resolved),
- Severity [and/or toxicity per protocol],
- Assessment of relatedness to talimogene laherparepvec or surgery, and
- Action taken.

The adverse event grading scale used will be the CTCAE version 3.0. The grading scale used in this study is described in [Appendix A](#). The investigator must assess whether the adverse event is possibly related to talimogene laherparepvec or surgery. This relationship is indicated by a "yes" or "no" response to the question: Is there a reasonable possibility that the event may have been caused by talimogene laherparepvec or surgery?

The investigator must assess whether the adverse event is possibly related to any study-mandated activity and/or procedure (including any screening procedures). This relationship is indicated by a "yes" or "no" response to the question: "Is there a reasonable possibility that the event may have been caused by a study activity and/or procedure"?

The investigator is responsible for reviewing laboratory test results and determining whether an abnormal value in an individual study subject represents a clinically significant change from the subject's baseline values. In general, abnormal laboratory findings without clinical significance (based on the investigator's judgment) are not to be recorded as adverse events. However, laboratory value changes that require treatment or adjustment in current therapy are considered adverse events. Where applicable,

clinical sequelae (not the laboratory abnormality) are to be recorded as the adverse event.

The investigator is expected to follow reported adverse events until stabilization or reversibility.

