9.2.2 Reporting Procedures for Serious Adverse Events

The investigator is responsible for ensuring that all serious adverse events observed by the investigator or reported by the subject that occur after signing of the informed consent through the safety follow-up (ie, 30 [+15] days after surgery) are recorded in the subject's medical record and are submitted to Amgen. All serious adverse events must be submitted to Amgen within 24 hours following the investigator's knowledge of the event via the applicable CRF.

After the protocol-required reporting period defined above, the investigator does not need to actively monitor subjects for serious adverse events. However, if the investigator becomes aware of a serious adverse event after this protocol-required reporting period, the investigator will report the event to Amgen within 24 hours following the investigator's knowledge of the event. Serious adverse events reported outside of the protocol-required reporting period will be captured within the safety database as clinical trial cases for the purposes of expedited reporting.

If the electronic data capture (EDC) system is unavailable to the site staff to report the serious adverse event, the information is to be reported to Amgen via an electronic Serious Adverse Event (eSAE) Contingency Report Form within 24 hours of the investigator's knowledge of the event. See [Appendix B](#) for a sample of the Serious Adverse Event Worksheet /eSAE Contingency Report Form. For EDC studies where the first notification of a Serious Adverse Event is reported to Amgen via the eSerious Adverse Event Contingency Report Form, the data must be entered into the EDC system when the system is again available.

The investigator must assess whether the serious adverse event is possibly related to talimogene laherparepvec or surgery. This relationship is indicated by a "yes" or "no" response to the question: Is there a reasonable possibility that the event may have been caused by talimogene laherparepvec or surgery?

The investigator must assess whether the serious adverse event is possibly related to any study-mandated activity or procedure. This relationship is indicated by a "yes" or

“no” response to the question: “Is there a reasonable possibility that the event may have been caused by a study activity/procedure”?

The investigator is expected to follow reported serious adverse events until stabilization or reversibility.

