If event occurred before the first dose of Investigational Product (IP)/drug under study, add a check mark in the corresponding box.

Is event serious?* – Indicate Yes or No. **This is a mandatory field.**

Serious Criteria Code* – **This is a mandatory field for serious events.** Enter all reasons why the reported event has met serious criteria:

- Immediately life-threatening – Use only if the subject was at immediate risk of death from the event as it occurred. Emergency treatment is often required to sustain life in this situation.
- If the investigator decides an event should be reported in an expedited manner, but it does not meet other serious criteria, "Other Medically Important Serious Event" may be the appropriate serious criterion.

Relationship to IP – The Investigator must determine and enter the relationship of the event to the IP at the time the event is initially reported. **This is a mandatory field.**

Relationship to Amgen device* – The Investigator must determine and enter the relationship of the event to the Amgen device (e.g. prefilled syringe, auto-injector) at the time the event is initially reported. **If the study involves an Amgen device, this is a mandatory field. This question does not apply to non-Amgen devices used in the study (e.g. heating pads, infusion pumps)**

Outcome of Event* – Enter the code for the outcome of the event at the time the form is completed. **This is a mandatory field.**

- Resolved – End date is known
- Not resolved / Unknown – End date is unknown
- Fatal – Event led to death

If event is related to a study procedure, such as a biopsy, radiotherapy or withdrawal of a current drug treatment during a wash-out period, add a check mark to the corresponding box. This does not include relationship to IP or concomitant medication – only diagnostic tests or activities mandated by the protocol.

4. Hospitalization

If the subject was hospitalized, enter admission and discharge dates. Hospitalization is any in-patient hospital admission for medical reasons, including an overnight stay in a healthcare facility, regardless of duration. A pre-existing condition that did

not worsen while on study which involved a hospitalization for an elective treatment, is not considered an adverse event. Protocol specified hospitalizations are exempt.

**Completion Instructions - Electronic Adverse Event Contingency Report Form
(for use for Studies using Electronic Data Capture [EDC])**

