3. SERIOUS ADVERSE EVENT

Provide the date the Investigator became aware of this information: Day ____ Month ____ Year ____

Serious Adverse Event diagnosis or syndrome If diagnosis is unknown, enter signs / symptoms and provide diagnosis, when known, in a follow-up report List one event per line. If event is fatal, enter the cause of death. Entry of "death" is not acceptable, as this is an outcome.	Date Started Day Month Year	Date Ended Day Month Year	Check only if event occurred before first dose of IP is event serious?	If serious, enter Serious Criteria code (see codes below)	Relationship Is there a reasonable possibility that the Event may have been caused by IP or an Amgen device used to administer the IP?								Outcome of Event Resolved Not resolved Fatal Unknown <small>eg, biopsy</small>	Check only if event is related to study procedure
					T.Vec		Device		<PIdvics>		<PIdvics>			
					Nov	Yes	Nov	Yes	Nov	Yes	Nov	Yes		
			 Yes  No											
			 Yes  No											
			 Yes  No											

Serious Criteria: 01 Fatal 02 Immediately life-threatening 03 Required/prolonged hospitalization 04 Persistent or significant disability /incapacity 05 Congenital anomaly / birth defect
 06 Other medically important serious event

4. Was subject hospitalized or was a hospitalization prolonged due this event? No Yes If yes, please complete all of Section 4

Date Admitted Day Month Year	Date Discharged Day Month Year
---------------------------------	-----------------------------------

5. Was IP/drug under study administered/taken prior to this event? No Yes If yes, please complete all of Section 5

IP/Amgen Device:	Date of Initial Dose Day Month Year	Prior to, or at time of Event				Action Taken with Product 01 Still being Administered 02 Permanently discontinued 03 Withheld	Lot # and Serial #
		Date of Dose Day Month Year	Dose	Route	Frequency		
Talimogene Laherparepvec  blinded  open label						Lot # _____  Unknown Serial # _____  Unavailable / Unknown	
<<IP/Device>>  blinded  open label						Lot # _____  Unknown Serial # _____  Unavailable /	

FORM-056006

Version 7.0 Effective Date: 1 February 2016

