## **10.6 Safety Analyses**

### **10.6.1 Adverse Events**

The Medical Dictionary for Regulatory Activities (MedDRA) version 19.1 or later will be used to code AEs to a system organ class (SOC) and a preferred term within the SOC. The CTCAE version 3.0 will be used to grade severity of AEs.

Only treatment-emergent adverse events (see [Section 6](#) for definition) will be summarized by treatment received. Subject incidence rates of all treatment-emergent, grade  $\geq 3$ , serious, non-serious, treatment related, serious treatment related, non-serious treatment related, events leading to talimogene laherparepvec withdrawal/delay/less than 4ml volume per administration, events leading to cancel the scheduled surgical removal of the melanoma tumor lesion(s), fatal adverse events and local effects on the lesion (i.e., pain, inflammation and ulceration) as well as adverse events of interest will be tabulated by SOC and PT in descending order of frequency within an SOC. For all treatment-emergent adverse events additional summary tables will also be provided by (1) SOC, PT in descending order of frequency within an SOC and worst CTCAE grade, and (2) PT in descending order of frequency.

In addition, certain categories of adverse events occurring within the talimogene laherparepvec monotherapy period and within the period after the start of the first dose of talimogene laherparepvec of  $10^6$  PFU/mL but before the first dose talimogene laherparepvec of  $10^8$  PFU/mL will be summarized separately by system organ class and preferred term in descending order of frequency. These categories of adverse events include all treatment-emergent adverse events, serious treatment-emergent adverse

events, non-serious treatment-emergent adverse events, talimogene laherparepvec related treatment-emergent adverse events.

Subgroups group analyses for age group (< 65, ≥ 65 and < 75, ≥ 75), sex, and race (white vs not white) will be presented for all treatment-emergent adverse events by system organ class and preferred term by treatment received in descending order of frequency.

Narratives of deaths through either the 30 days after the last dose of talimogene laherparepvec or the surgical resection of melanoma tumor lesion(s), whichever is later, will be provided.

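### As the protocol is written, one causality answer covers drug or surgery, so in Arm 1 events from surgery to the safety follow-up visit cannot be attributed to the drug specifically

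*Protocol*

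**What the plan says.** Protocol 9.2.1 (non-serious events) lists one relatedness attribute that joins the drug and surgery. It is answered yes or no to "Is there a reasonable possibility that the event may have been caused by talimogene laherparepvec or surgery". Section 9.2.2 does the same for serious events: "The investigator must assess whether the serious adverse event is possibly related to talimogene laherparepvec or surgery". Both sections add a second yes/no question on study conduct, which in 9.2.1 reads "Is there a reasonable possibility that the event may have been caused by a study activity and/or procedure".

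The Appendix B contingency form, for use when electronic data capture (EDC) is unavailable, asks a different question: "Is there a reasonable possibility that the Event may have been caused by IP or an Amgen device used to administer the IP". It has a No/Yes column for the drug and a separate box for events related to a study procedure. Its instructions say: "The Investigator must determine and enter the relationship of the event to the IP at the time the event is initially reported".

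The incidence of treatment-related adverse events is a safety endpoint (Protocol 10.1.1.2). The rationale in Protocol 2.3 states a particular interest: "Also, safety of talimogene laherparepvec, especially related to postoperative complications will be evaluated".

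SAP 10.6.1 tabulates treatment-related events by treatment received, without dividing them by cause. It names "talimogene laherparepvec related treatment-emergent adverse events" only for two windows: the monotherapy period, and the interval from the first 10^6 PFU/mL dose to the first 10^8 PFU/mL dose. Post-surgery events are to be summarized, but no drug-specific category is named for them. SAP Section 6 does not define treatment-related.

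**The concern.** Every Arm 1 subject who is injected and then resected has been exposed to both candidate causes, and the two can lie close together. Surgery may follow the last dose by as little as about one week (Protocol 3.1). Some effects reported for the drug resemble postoperative events. Protocol 2.2 gives pyrexia in 43% of treated subjects in the earlier phase 3 trial, and grade 3/4 cellulitis in 6 subjects (2.1%). The surgical safety evaluation in Protocol 7.2.3 looks for postoperative infection and wound-closure problems. For a postoperative fever or cellulitis, a yes to the combined question does not say which cause the investigator suspected.

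At stake is the meaning of the Arm 1 treatment-related rate after surgery, in the period that the rationale singles out. The mismatched back-up form adds a smaller problem: two truthful answers about the same serious event can differ because the questions differ.

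**Working it through.** No arithmetic tests this point. The check sets the questions side by side and asks what each answer can mean.

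**By arm and period**

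| Period | Arm 1: what a yes means | Arm 2: what a yes means |
|---|---|---|
| Before surgery | In effect the drug, since surgery has not happened | Neither treatment has been given |
| Surgery to the safety visit, 30 (+15) days | Drug, surgery or both | Surgery only |
| Long-term follow-up | Drug only: Protocol 7.2.4 collects events judged potentially drug-related | Not collected |

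The ambiguity therefore sits in one cell. At 1:1 allocation of about 150 subjects, Arm 1 holds about 150 / 2 = 75, fewer any who are not resected. Only the part up to 30 days after surgery normally enters the treatment-emergent tables, because the SAP Section 6 treatment period ends there.

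**By true suspected cause, within that cell**

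| Suspected cause | Combined question (9.2.1, 9.2.2) | Study activity/procedure question, if sites count the resection | Contingency form, drug column |
|---|---|---|---|
| Drug only | Yes | No | Yes |
| Surgery only | Yes | Yes | No |
| Both | Yes | Yes | Yes |

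1. The combined question gives the same answer in all three rows.
2. The study activity/procedure question does not repair this. Protocol 6.3 lists the resection as a protocol-required therapy, and the protocol does not say that it counts as a study activity or procedure. Even if every site counted it, surgery alone and surgery plus drug would give the same pair of answers, so drug involvement is still not isolated.
3. For a surgery-only serious event, 9.2.2 calls for yes and the contingency form's drug column calls for no. The form's study-procedure box may be ticked as well. Its instructions confine it to mandated diagnostic tests or activities, yet give radiotherapy as an example, so it is unclear whether the resection belongs there.
4. Section 9.2.2 requires contingency reports to be entered in EDC later and requires consistency with the CRF. The mismatch therefore has to be settled at entry, and the text gives no rule for doing so.

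**Against the planned tables.** Both SAP windows with a drug-related table end before surgery. The monotherapy period stops at the earlier of surgery or 30 days after the last dose (SAP Section 6). In those windows the combined answer is sufficient. The answer loses its meaning as a drug attribution only in the overall treatment-related tables and in any post-surgery table.

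**The case against.** The strongest case against runs as follows.

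- **The CRF is unseen.** The SAP's drug-related category and the drug column on the contingency form are both compatible with a drug-specific field in the database. This stands. The point concerns the protocol text, not the data.
- **The combined definition is coherent.** SAP 7.2 compares regimens, and relatedness to drug or surgery is a natural regimen-level definition that gives Arm 2 a comparable rate. This also stands, so the union should be kept. It does not answer why the components should go unrecorded.
- **Randomization answers the safety question.** Both arms have surgery and the same surgical safety evaluation, and Protocol 10.5.4 and SAP 10.6.1 provide for post-surgery summaries. An Arm 1 excess of postoperative events would show without open-label investigator attribution. This stands at group level. It does not give attribution for an individual event.
- **The form is a restricted back-up.** Its reports must be entered in EDC, and it has a procedure box. This reduces the mismatch to one of wording that needs reconciling.

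A reader might infer three stronger things. The first is that the drug's postoperative safety cannot be evaluated; the control arm shows otherwise. The second is that serious events will end up in the database with a causality that depends on reporting route; the EDC-entry and consistency rules do not support that. The third is that the Arm 1 treatment-related rate is inflated by a calculable amount; the documents give no rates of surgery-related events, and the combined rate is a correct value for a regimen-level endpoint.

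**Conclusion.** The point holds in a limited form. The protocol prescribes one answer for two causes. In Arm 1, from surgery through the safety follow-up visit, that answer cannot separate drug-related from surgery-related events, and nothing else prescribed does so. Pre-surgery events (by timing) and long-term follow-up events (collected as drug-related) are unaffected. The contingency form's question differs from 9.2.2 and needs reconciling.

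The size cannot be given as a rate. What is lost is event-level drug attribution in one window of one arm, for a stated safety endpoint. The primary endpoint, the sample size and the between-arm comparison of postoperative events are untouched. The conclusion assumes that the CRF follows the protocol wording. If it already has two fields, the defect is only that the text misdescribes it. This is a worthwhile, inexpensive improvement rather than a flaw that undermines the trial.

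**What to change.** Replace the combined question with two yes/no items: (a) whether talimogene laherparepvec may have caused the event, asked in Arm 1 only, and (b) whether surgery may have caused it. Use identical wording in Protocol 9.2.1 and 9.2.2, the CRF and the Appendix B form.

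In SAP 10.6.1, define treatment-related as a yes to either item; in Arm 2 this reduces to item (b). Also tabulate drug-related and surgery-related events separately, before and after surgery.

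The cost is one extra CRF field, the wording changes, and one more causality judgement per event. The current text is a March 2018 amendment of a May 2014 protocol with about 18 months of planned accrual, so many events may already be recorded. If the CRF has only the combined field, Arm 1 post-surgery events answered yes would need re-query. Those answered no would not, because no to the union is no to both. If the CRF already has both items, only the documents change.

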9.2.2 Reporting Procedures for Serious Adverse Events

The investigator is responsible for ensuring that all serious adverse events observed by the investigator or reported by the subject that occur after signing of the informed consent through the safety follow-up (ie, 30 [+15] days after surgery) are recorded in the subject's medical record and are submitted to Amgen. All serious adverse events must be submitted to Amgen within 24 hours following the investigator's knowledge of the event via the applicable CRF.

After the protocol-required reporting period defined above, the investigator does not need to actively monitor subjects for serious adverse events. However, if the investigator becomes aware of a serious adverse event after this protocol-required reporting period, the investigator will report the event to Amgen within 24 hours following the investigator's knowledge of the event. Serious adverse events reported outside of the protocol-required reporting period will be captured within the safety database as clinical trial cases for the purposes of expedited reporting.

If the electronic data capture (EDC) system is unavailable to the site staff to report the serious adverse event, the information is to be reported to Amgen via an electronic Serious Adverse Event (eSAE) Contingency Report Form within 24 hours of the investigator's knowledge of the event. See [Appendix B](#) for a sample of the Serious Adverse Event Worksheet /eSAE Contingency Report Form. For EDC studies where the first notification of a Serious Adverse Event is reported to Amgen via the eSerious Adverse Event Contingency Report Form, the data must be entered into the EDC system when the system is again available.

The investigator must assess whether the serious adverse event is possibly related to talimogene laherparepvec or surgery. This relationship is indicated by a "yes" or "no" response to the question: Is there a reasonable possibility that the event may have been caused by talimogene laherparepvec or surgery?

The investigator must assess whether the serious adverse event is possibly related to any study-mandated activity or procedure. This relationship is indicated by a "yes" or

“no” response to the question: “Is there a reasonable possibility that the event may have been caused by a study activity/procedure”?

The investigator is expected to follow reported serious adverse events until stabilization or reversibility.

New information relating to a previously reported serious adverse event must be submitted to Amgen. All new information for serious adverse events must be sent to Amgen within 24 hours following knowledge of the new information. The investigator may be asked to provide additional follow-up information, which may include a discharge summary or extracts from the medical record. Information provided about the serious adverse event must be consistent with that recorded on the applicable CRF (eg, Adverse Event Summary CRF).

If a subject is permanently withdrawn from protocol-required therapies because of a serious adverse event, this information must be submitted to Amgen.

Amgen will report serious adverse events and/or suspected unexpected serious adverse reactions as required to regulatory authorities, investigators/institutions, and IRBs/IECs in compliance with all reporting requirements according to local regulations and good clinical practice (GCP).

The investigator is to notify the appropriate IRB/IEC of serious adverse events occurring at the site and other adverse event reports received from Amgen, in accordance with local procedures and statutes.

